1.0 BACKGROUND

A stable tear film is essential for good visual function. On the other hand, excessive tearing (i.e., **epiphora** – a very common condition [1]) can be a major cause for loss of quality of life [2], interfering with activities such as driving, reading, watching TV, being outdoors, and social interactions, in addition to being a major risk for tear duct infection (dacryocystitis), especially in children [3]. The constant dabbing of the cheeks can also lead to skin irritation and puts the eyes at risk of infection. While the prevalence of epiphora is not known, the incidence of symptomatic nasolacrimal duct obstruction in 1996-2000 in the US was 30.47 per 100,000, or approximately 120,000 new cases per year [1]. Globally, the incidence is even higher, with case series publications from India, Singapore and South Korea suggesting a significant global disease burden. In the treatment of epiphora, and in order to facilitate proper healing, surgeons frequently place a temporary silicone tube within the healing lacrimal drainage system to stent the passages during the healing process [4-7]. Many thousands of these procedures are performed each year, and the longer the stents stay in place, the higher the likelihood of long-term surgical success [8-11]. However, the stents occupy space within the very narrow lacrimal drainage apparatus, delaying maximal improvement in tear drainage until the stent is removed weeks to months after the procedure. This issue is further exacerbated in cancer patients on chemotherapy such as docetaxel (Taxotere) chemotherapy for breast cancer [12], which requires prolonged stenting. Despite the fact that stents have a hollow lumen, there are no stents on the market in which the lumen is open to tear drainage – possibly because of the engineering challenge of creating an opening into the lumen that is large enough to allow tears to flow in but not so large that the stent becomes too weak and fragile that it breaks prematurely. Through an active collaboration between an ophthalmologist and a mechanical engineer, we have developed a lacrimal stent that has a slit opening strategically constructed to drain tears into the lumen, while optimizing the basic characteristics of the silicone tubing for the purpose of intraluminal drainage. Such a stent could revolutionize the use of stents in the treatment of symptomatic, debilitating epiphora.

1.1 Preliminary Clinical Data / Prior Clinical Experience

This study is of the Slit Stent II medical device, a novel variation on a well-established surgical tool, namely a silicone tube used to temporarily stent the lacrimal drainage system following a recanalization procedure to treat epiphora. Hence, its use in human patients is based on a solid clinical foundation [see literature summary below.] Silicone stents have been used successfully for decades to maintain the patency of the lacrimal drainage apparatus as the tissues heal following dacryocystorhinostomy (DCR) surgery. The Slit Stent II is a modification of the “BIKA for DCR” silicone stent manufactured by FCI (FCI SAS; Besancon, France) and approved for use throughout the world, including in the United States [13-16].

Literature has reported the use of lacrimal stents since 1998 [6, 9, 14, 17-19]. In the following 20 years, multiple articles involving over 1,000 patient subjects have examined DCR with and without stents, with techniques involving polyurethane or silicone stents, using bicanalicular or monocanalicular stents [3-7, 9-11, 16, 20-40]. In 2016, Fayers *et al* reported a prospective, randomized, controlled, interventional trial involving 300 adult subjects, half of whom received

bicanalicular stents, concluded that there is a statistically significantly higher success rate in EN-DCR surgery with stents compared with no stent [31].

The specific stent used in this study (without our modifications, however) is the subject of four prior publications involving 485 adult subjects [13-16]. As previously mentioned, this is the BIKA for DCR bicanalicular stent manufactured by FCI SAS, Besancon, France. These publications looked at the relative success and complications of monocalicular stents versus bicanalicular stents; external DCR versus endonasal DCR; and the unciformian endonasal technique versus the maxillary endonasal technique. Of note is that in all cases the silicone stent, BIKA for DCR, was used as the standard and its use was routine.

1.2 Rationale for Study and Use of the Slit Stent II Device

The Slit Stent II has an internal lumen that is open to the ocular surface at the interpalpebral fissure, such that tears can drain through the lumen of the stent. After it is placed into the lacrimal system and into the nose, the slit openings into the lumen will allow tears to drain into the nose, which is where tears normally drain, rather than flow over the lid margin and onto the cheek (epiphora).

2.0 PRODUCT DESCRIPTION

2.1 Intended Use

Temporary post DCR lacrimal stenting

2.2 Indications for Use

Nasal bicanalicular intubation is indicated in treatment of epiphora in adults in cases of Dacryocystorhinostomy (conventional or laser).

2.3 Device Description

A lacrimal stent is hollow silicone tubing with a non-traumatic tip. The tubing is securely attached into malleable stainless steel probes that are used to guide the silicone tubing through the lacrimal drainage apparatus. The device is used to maintain an open lacrimal path between the surface of the eye and the nasal passages, particularly during a healing process following injury or surgery.

The BIKA for DCR lacrimal stent is a bicanalicular intubation device used for intubation of the lacrimal drainage apparatus, especially in cases of dacryocystorhinostomy (conventional or laser). The silicone tube acts as a conformer during the healing process while facilitating drainage of tears

through capillary action around the stent. In cases of canalicular lacerations, the silicone tube guides wound healing and prevents the onset of synechia.

The BIKA lacrimal stent consists of a single unit including a silicone tube (length: 280 mm, external diameter: 0.94 mm), and one steel probe at each end of the silicone tube (length: 53 mm, external diameter: 0.8 mm) with round tips (see Figure 1, below).

[figure not shown]

Fig. 1: BIKA for DCR

The BIKA for DCR is a sterile, single-use device, and is an FDA cleared device.

The Slit Stent II (investigational) device is created by modifying an existing FDA cleared lacrimal stent (Bika, manufactured by FCI Ophthalmics- see figure 1 above) by adding additional 3 mm (\pm 0.5 mm) and 35 mm (\pm 3.5 mm) long slits of equal depth. See figure 2 below.

Figure 2. A 3 mm long slit into the silicone tubing.

The axial cutouts located on the stent allow drainage of tears from the ocular surface to the nasal/oropharynx cavities through the internal lumen of the stent. See figure 3.

[figure not shown]

Figure 3. Stent with multiple cut-outs placed as part of a standard DCR procedure allow for improved draining of tears and resolution of symptomatic tearing.

All modifications to the stent are inspected under an optical microscope at a magnification of at least 5x to ensure they are free from cutting defects, which could impact the structural integrity of the Slit Stent II. To ensure that the Slit Stent II can withstand the forces experienced during implantation and removal, additional mechanical integrity tests were performed. Comparing the implantation forces to the maximum insertion and removal force, we determined that the modified Slit Stent II will have excellent tensile strength – essentially identical to unmodified stent – to prevent mechanical failure in patient use. Each section was tested to determine the maximum elongation and force it can withstand before failure.

After modification at the University of Michigan, the Slit Stent II is then packaged and sent to FCI Ophthalmics for sterilization, packaging and return to Michigan for use in the clinical trial.

3.0 RISK/BENEFIT ANALYSIS

3.1 Comparison with Other Alternative Devices

Devices for post-DCR temporary stenting are ubiquitous and widely used. There are no foreseeable risks for the modified slit stents beyond the standard risks associated with DCR with stenting.

As in any type of surgery, there are risks linked to the material or to developments of the initial pathology. Potential complications associated with the placement of the BIKA for DCR stents include, but are not limited to the following:

Post-operative complications:

- bleeding from nose
- infection
- conjunctival or nasal pruritus
- nasal mucosa or caruncular irritation
- reversible shrinkage of the palpebral fissure
- exteriorization or loss of the stent tubing
- punctal/canalicular injury
- canaliculitis

Device related complications could include, but are not limited to:

- Device dislocation into the oropharynx
- Corneal abrasion
- Conjunctival abrasion
- Secondary surgical interventions related to the Slit Stent II device (surgical repositioning, removal, or replacement)

This is the only device that will allow tears to drain through the lumen.

3.2 *Minimization of Potential Risks*

Standard surgical technique will be used. Post-operative ocular surface antibiotic drops will be used in the usual manner. Subjects will be observed closely to detect any adverse events or complications that may have occurred.

3.3 *Potential Benefits*

Benefits include more rapid resolution of epiphora symptoms and longer retention of the stent for a better long-term surgical outcome.

3.4 *Justification for the Investigation*

- Investigate whether a stent with slits at the interpalpebral fissure is well tolerated
- Determine whether epiphora improves following DCR and Slit Stent II placement

4.0 OBJECTIVES

- 1) Assess tolerance of patients to placement of Slit Stent II (Glasgow Benefits Index and Patient Stent Tolerance and Irritation Assessment)
- 2) Assess ocular surface irritation (objective and subjective) following stent placement (Glasgow Benefits Index and Patient Stent Tolerance and Irritation Assessment; Conjunctival and corneal epithelial surface exam and staining under the slit lamp)
- 3) Assess change in quality of life following surgery (Glasgow Benefits Index and Lac-Q Questionnaire)
- 4) Assess change in tearing/epiphora symptoms before and after surgery (Glasgow Benefits Index and Lac-Q Questionnaire)

- 5) Assess change in conjunctival tear lake measurement before and after surgery
- 6) Assess bacterial growth on stents after removal

All criteria will be summarized within the Slit Stent II treatment group. Formal comparisons will be made to no treatment effect and to the standard treatment (control group).

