10.5.2 Glasgow Benefit Inventory (GBI) Questionnaire

The effectiveness parameter evaluated will be the mean composite score for the GBI administered post-treatment at the 1-4 month post-operative follow-up visit. The GBI will be administered at each post-operative visit. It is believed that the positive effect of the surgery will have manifested itself in GBI score by the 2nd follow-up visit. A 95% t confidence interval will be used to estimate the mean score.

Scoring the GBI will follow the standard protocol (**Appendix A**). Positive scores indicate improvement from pre-treatment; negative scores indicate deterioration.

As part of the GBI protocol, it is expected that researchers may need to change the format or appearance of items to suit their purposes.

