10.5.3. Lac-Q Questionnaire (Appendix B)

This study does not aim to assess the effectiveness of the DCR procedure, which is a well-established surgical procedure for the treatment of epiphora secondary to nasolacrimal duct obstruction. Furthermore, the study does not aim to assess the effectiveness of using a silicone lacrimal stent as part of a lacrimal procedure. Rather, the primary goal of this study is to assess patient tolerance of the Slit Stent II, which introduces novel cuts into the traditional stent that allow for intraluminal tear drainage. The secondary goal of the study is to confirm that the Slit Stent II functions like any other silicone lacrimal stent as an adjunct to a lacrimal procedure. The effectiveness of the procedure in relieving the tearing symptoms and associated social isolation will be assessed at the pre-op visit and at each post-op visit. Scoring will follow the standard protocol (**Appendix B**). The Lac-Q questionnaire will always be given first among the questionnaires.

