Since your operation, have you found it easier or harder to deal with company?

Since your received your hearing aid, have you found it easier or harder to deal with company?

Since your speech therapy, have you found it easier or harder to deal with company?

Does the condition of your nose affect how you deal with company?

Scoring

The response to each question is based on a five-point Likert scale ranging from a large deterioration in health status through to a large improvement in health status, (see example below).

1. Has the result of the operation/intervention* affected the things you do?				
Much worse	A little or somewhat worse	No change	A little or somewhat better	Much better
1	2	3	4	5

To help control for response bias, half of the questions have the answers ranging from a large improvement to a large deterioration while the other half range the other way. The GBI questionnaire is scored into a total score and also 3 subscales:- a general subscale, (12 questions), a social support subscale, (3 questions), and a physical health subscale, (3 questions). All these scores range from -100 to +100.

Score all questions so that a score of 1 is given to the answer with the worst change in health status and 5 to the answer with the best change in health status.

Total Score

- Sum all the responses (Qu. 1-18)
- Divide by 18 (to obtain an average response score)
- Subtract 3 from the average response score
- Multiply by 50.

General Subscale Score

- Sum 12 of the responses (Qu. 1,2,3,4,5,6,9,10,14,16,17 and 18)
- Divide by 12 (to obtain an average response score)
- Subtract 3 from the average response score
- Multiply by 50.

Social Support Score

- Sum 3 of the responses (Qu. 7,11,15)
- Divide by 3(to obtain an average response score)
- Subtract 3 from the average response score
- Multiply by 50.

Physical Health Score

- Sum 3 of the responses (Qu. 8,12,13)
- Divide by 3(to obtain an average response score)
- Subtract 3 from the average response score
- Multiply by 50.

The GBI questionnaire (Modified for this study):

1. Has the result of the tear duct surgery affected the things you do?

Much worse	A little or somewhat worse	No change	A little or somewhat better	Much better
1	2	3	4	5

2. Have the results of the tear duct surgery made your overall life better or worse?

Much better	A little or somewhat better	No change	A little or somewhat worse	Much worse
5	4	3	2	1

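### Section 10.5.2 defines the GBI effectiveness parameter as a single mean, and 4.0 ranks a test against no effect equally with the control comparison; neither says that the between-arm difference governs the conclusion

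*Combined protocol and SAP*

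**What the plan says.** Section 4.0 closes its list of six objectives with one sentence on inference: "Formal comparisons will be made to no treatment effect and to the standard treatment (control group"). Both comparisons are called formal, the one with no effect comes first, and neither is given priority.

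Section 10.5 names symptom change and GBI quality of life as the primary effectiveness outcomes. Section 10.5.2 makes the GBI specific: "The effectiveness parameter evaluated will be the mean composite score for the GBI administered post-treatment at the 1-4 month post-operative follow-up visit". The estimator is a single-mean interval: "A 95% t confidence interval will be used to estimate the mean score". On direction it says "Positive scores indicate improvement from pre-treatment; negative scores indicate deterioration", so zero means no change since before surgery. It names no difference between arms and no margin.

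Other sections point to the between-arm contrast. Section 10.0 plans 95% intervals for each arm and for the difference, and singles out the difference intervals as what will show similarity to BIKA. Section 10.1 sizes the trial on GBI non-inferiority to BIKA with a 20-point margin. Section 10.5.3 gives the goals as tolerance of the new stent and confirmation that it works as other silicone stents do. It also sets out what is not an aim: "This study does not aim to assess the effectiveness of the DCR procedure", and "the study does not aim to assess the effectiveness of using a silicone lacrimal stent as part of a lacrimal procedure".

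**The concern.** All 50 subjects have DCR with a silicone stent; only the slits differ between arms. The GBI items in Appendix A ask about the operation, for example "Have the results of the tear duct surgery made your overall life better or worse", and 10.5.2 itself credits the expected score to surgery: "It is believed that the positive effect of the surgery will have manifested itself in GBI score by the 2nd follow-up visit". A Slit Stent II mean above zero is therefore the joint result of DCR, stenting and any non-specific change over time. It does not isolate the slits and does not say whether the device does as well as BIKA.

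At stake is which result decides effectiveness. A reader who follows 10.5.2 and the first comparison in 4.0 would look at one arm against zero. A reader who follows 10.0 and 10.1 would look at the difference against the margin. The two can disagree, and the plan does not say which one governs.

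**Working it through.** **Inputs from the documents.** 25 subjects per arm (7.0, 10.1); GBI SD about 25, margin 20, true difference 0, stated power 87% (10.1); two-sided 5% for all tests and intervals (10.0).

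**Assumed.** The documents give no expected mean GBI, so a range of BIKA means is used.

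**Step 1: reproduce the plan's power.** The standard error of the difference is 25 × √(2/25) = 7.07. The noncentrality at true difference 0 is 20 / 7.07 = 2.83, with 48 degrees of freedom.

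- One-sided 5%: 87.4% by noncentral t (88.2% by the normal approximation). This matches the stated 87%.
- One-sided 2.5%, which is a two-sided 95% interval read against the margin: 79.2% (80.7% by the normal approximation). This does not match.

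The stated figure is therefore a between-arm calculation at one-sided 5%.

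**Step 2: the test of one arm against zero.** The standard error of the mean is 25 / √25 = 5. The two-sided 5% critical value on 24 degrees of freedom is 2.064, so with a sample SD of 25 the result is positive once the observed mean passes 2.064 × 5 = 10.3 points. For a true mean μ, the chance of a positive result is P(T > 2.064), where T is noncentral t with 24 degrees of freedom and noncentrality μ/5.

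**Step 3: set the device exactly 20 points below BIKA.** This is the edge of the plan's own margin.

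| Assumed BIKA mean | Slit Stent II mean | Noncentrality | Within-arm test positive | Non-inferiority shown (one-sided 2.5% / 5%) |
|---|---|---|---|---|
| 25 | 5 | 1 | 16% | 2.5% / 5% |
| 30 | 10 | 2 | 48% | 2.5% / 5% |
| 35 | 15 | 3 | 82% | 2.5% / 5% |
| 40 | 20 | 4 | 97% | 2.5% / 5% |

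The last column does not depend on the BIKA mean, because the difference is fixed at the margin. The within-arm column depends on it almost entirely.

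**Step 4: where a null of no effect has a meaning.** By Appendix D and 9.1.3, Lac-Q and the slit-lamp tear lake are measured before and after surgery, and the GBI is scored as change from before surgery. The stent tolerance and irritation assessment and the stent culture exist only after implantation. For those, the blanket comparison in 4.0 has no defined null.

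**The case against.** The strongest reply is that the between-arm analysis is already planned. The sentence in 4.0 includes the control comparison, 10.0 gives the difference intervals the leading role, and 10.1 sizes the trial on non-inferiority. On this view 10.5.2 only names the variable, summary and visit, and 10.0 supplies the contrast. It never says that one arm will be tested against zero. This stands in part. A reader might infer that the plan lacks a controlled comparison or means to claim effectiveness from one arm; the documents support neither. What remains is that the section defining a primary effectiveness outcome omits the contrast and the margin, and 4.0 does not rank its two comparisons.

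It can also be said that before-after change is a stated aim. Section 3.4 asks whether epiphora improves after DCR with the Slit Stent II, and objectives 3 to 5 concern change after surgery. This stands. It would go too far to say that the within-arm result merely tests DCR, carries no information, or must be deleted. It describes the outcome of DCR and Slit Stent II together, which those objectives ask for.

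Finally, the size depends on a mean that the plan does not give. This also stands: at an assumed BIKA mean of 25, the within-arm test would be positive only 16% of the time.

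**Conclusion.** The point holds as an inconsistent and unranked definition of the effectiveness result, not as a missing comparison. A positive Slit Stent II mean GBI is compatible with a device at the edge of the non-inferiority margin: the chance is 16% to 97% over assumed BIKA means of 25 to 40, against at most 5% for the between-arm test. These figures rest on the plan's SD of 25, complete data on 25 per arm, and assumed means. A reader might infer that the within-arm test would be positive however poor the device; that is true only where the assumed means are high.

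Section 10.0 leaves methods to a detailed SAP that takes precedence over the protocol. That SAP could settle the matter, but the text supplied does not.

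**What to change.** In 10.5.2, define the effectiveness parameter as the Slit Stent II minus BIKA difference in mean GBI at the day 30-120 visit, with its 95% confidence interval read against -20. Keep the mean and interval for each arm as description.

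In 4.0, state that the comparison with control governs the effectiveness conclusion. State also that comparisons with no effect (GBI, Lac-Q, tear lake) are supportive or descriptive, answer objectives 3 to 5 only, and do not apply to measures without a pre-operative value. Carry the same wording into the detailed SAP.

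The cost is wording; no visit or measurement is added. The within-arm result no longer counts as evidence of device effectiveness. The change also exposes a mismatch already in the plan: with the two-sided 5% level of 10.0, non-inferiority power at 25 per arm is about 79%, and the stated 87% corresponds to one-sided 5%. Sections 10.0 and 10.1 should be made to agree. For scale, 87% power at one-sided 2.5% needs about 2 × 25² × (1.96 + 1.126)² / 20² = 29.8, or 30 per arm, by the normal approximation and before any dropout.

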5.0 OUTCOMES ASSESSMENT TIMETABLE

Patients will be assessed at 1-day post op by phone, and exams at 5-14 days post-DCR surgery (1st post-op visit), 2-4 months post-DCR surgery (usually 2nd post-op visit), and 4-7 months post-DCR surgery.

6.0 STUDY DESIGN

Double arm, single blind, prospective randomized study

7.0 SUBJECT POPULATION

This is a single center study that will be conducted at the University of Michigan (Ann Arbor, Michigan). Fifty (50) subjects will be enrolled and treated with either the experimental Slit Stent II (25 patients) or the control stent BIKA for DCR (25 patients). Patients who are currently scheduled to undergo a DCR (dacryocystorhinostomy) as per standard of care will be offered participation in the study. Patients who elect to participate in the study will be consented and then randomized to the treatment or control arm.

